**A Prospective Randomized Control Trial of The Effectiveness of Entereg as a Rescue Treatment of
Postoperative Ileus Following Colorectal Surgery**

NCT02742181

November 17, 2016

Primary Investigator:
[name]
[name]
[name]
P: [contact]
F: [contact]
[contact]

Co-Investigators:
[name]
[name]
[name]
[name]

Objectives

Primary:

- To determine the efficacy and safety of Entereg for the treatment of post operative ileus following colon or rectal resection.

Secondary

- To determine the effect of Entereg as rescue therapy postoperative ileus on hospital length of stay, return of bowel function, and 30-day outcomes.

Clinical hypotheses

Entereg can be given to patients after the development of post operative ileus to reduce the duration of ileus and shorten hospital stay.

Postoperative ileus (POI) is one of the most common complications following abdominal surgery, and a frequent cause of prolonged hospitalization ¹. The exact mechanisms of POI, defined as the prolonged transient impairment of bowel motility, are not well defined and are likely multifactorial ^{2,3}. The most commonly cited factors leading to the development of POI are disorganized electrical activity, sympathetic inhibitory neural reflexes, release of proinflammatory mediators, excessive intravascular volume, and the use of opioid analgesia ^{4,5}.

A variety of perioperative strategies have been developed to help prevent the development of and/or reduce the duration of POI. These strategies have been incorporated into most Enhanced Recovery After Surgery (ERAS) pathways, and include avoidance of mechanical bowel preparation, use of laparoscopy when feasible, IV fluid restriction, no routine nasogastric tube placement, early feeding and ambulation after surgery, and limiting opioid use ^{6,7}. Several pharmacologic agents have been studied as means to prevent POI. The most successful of these is Entereg, a peripheral opioid antagonist, currently approved for use in open bowel resection. Given preoperatively and continued postoperatively until return of bowel function, Entereg has been shown to reduce the incidence of POI, shorten hospital stay, and is associated with lower postoperative morbidity and readmissions compared to placebo ⁸⁻¹⁰.

Currently there are no effective treatments for POI ileus after it develops.

Numerous prokinetic agents, including erythromycin, cholecystokinin, lidocaine, and neostigmine, have been used in randomized control trials, yet none have been shown to reduce the duration of POI ¹¹. The use of laxatives has also been investigated as a potential treatment for POI. In one randomized trial, the use of bisacodyl after surgery led to significantly accelerated gastrointestinal recovery compared to placebo, however, the trial included all patients undergoing surgery and not just those who developed POI, and so the benefit of laxatives as a treatment modality remains unclear ¹².

Despite significant advances in prevention, POI continues to be a clinical issue. In our own practice, despite a robust ERAS pathway, POI occurs in approximately 10% of patients undergoing bowel resection, increasing hospital stay by an average of five days. For these patients, current treatment includes bowel rest, reduction of oral diet, and possible nasogastric tube placement while waiting for the

POI to resolve directed pharmacologic treatment could potential expedite the return of bowel function, reducing length of stay and increasing patient comfort.

The benefits of developing a treatment for post operative ileus are substantial. As opposed to prophylactic treatment, all patients without contraindications could be treated. This would reduce the use of unnecessary treatments in patients who do not develop POI. The decrease in patient discomfort, prolonged hospital stay would be significant. In addition, there is a financial cost to POI. The Health Care Financing Administration estimates that \$1.14 billion dollars are spent annual on postoperative ileus.

Despite extensive evidence for use in the prevention of POI, no formal studies have been performed to investigate the efficacy of Entereg as a rescue treatment of ileus after it develops. However, based on our use of Entereg inpatients with postoperative ileus, we have seen a rapid return of bowel function, decrease in placement of nasogastric tube and earlier discharge from hospital. A randomized control trial would provide concrete evidence of this anecdotal success and potentially lead to the first clinically effective pharmacologic rescue therapy of POI.

Study Overview

This will be a prospective randomized control trial with a total of 142 patients. Patients who undergo laparoscopic or open colorectal resection, small bowel resection, or ileostomy reversal with small bowel resection that subsequently develop postoperative ileus will be eligible for enrollment. If they meet inclusion/exclusion criteria, they will be randomized at the time of diagnosis of postoperative ileus to receive Entereg as rescue therapy or to receive conservative standard care.

Patients randomized to the Entereg group will be given 12mg of Entereg two times daily from the time of randomization until the return of bowel function or 5 days. Both groups will be treated with conservative standard care, including bowel rest, reduction in oral diet, and placement of nasogastric tube as clinically indicated.

All patients will follow a standard ERAS pathway after surgery, with early feeding and ambulation, along with opioid minimizing measures as is our standard postoperative protocol.

Primary outcome will be hospital length of stay.

Secondary outcomes will include time to return of bowel function, 30-day morbidity/mortality, complications, reoperation and readmission.

Total number of patients: 142

Patients in each study group: 71

Inclusion criteria

1. Subjects who have benign or malignant colonic or rectal disease that have undergone laparoscopic or open colorectal resection, small bowel resection or ileostomy reversal with small bowel resection and subsequently developed postoperative ileus, defined as:
 - a. Return to NPO status after initial diet attempts, or
 - b. Placement of nasogastric tube
2. Subjects who are 18 years of age and older
3. Subjects of either gender
4. Subjects who are willing and able to adhere to protocol requirements, agree to participate in the study program and provide written and informed consent.

Exclusion criteria

1. Subjects who received Entereg preoperatively.
2. Subjects that have taken therapeutic doses of opioids for more than 7 days immediately prior to surgery.
3. Subjects with severe hepatic impairment.
4. Subjects with end-stage renal disease.
5. Subjects who are pregnant.

6. Subjects who were diagnosed with a complete small bowel obstruction preoperatively.
7. Subjects with a medical condition that may interfere with the use of the study medication Entereg.
8. Subjects who have a condition or general disability or infirmity that in the opinion of the investigator precludes further participation in the study
9. Subjects with an ostomy

Study Calendar	Screening	Remaining Hospitalization	30 Day Follow-up
Enrollment Criteria	x	x	
Study Group Assignment	x		
Informed Consent	x		
History and Physical	x		
Collection of demographic data	x	x	
Monitoring for return of bowel function		x	
Administration of Entereg 12mg PO BID or conservative management		x (until return of bowel function)	
Enhanced Recovery Program (ERP)		x	
Complications/ Adverse events		x	x

Recruitment

Patients will be recruited from the University Hospitals Case Medical Center Division of Colorectal Surgery in Cleveland, OH. The patient population in this study will be candidates of either sex, over 18, who have benign or malignant colonic or rectal disease in which resection was performed via an open or laparoscopic approach, small bowel resection or ileostomy reversal with small bowel resection and primary anastomosis and subsequently developed postoperative ileus. The diagnosis of postoperative ileus will be made by meeting one or more of the following criteria: 1) return to NPO status after initial attempts at oral diet, 2) placement of nasogastric tube after surgery. Patients will be recruited until at least 142 participants are enrolled unless the study is halted prematurely by the safety monitoring board. The investigators will discuss the study with potential subjects prior to surgery date. The potential subjects will be given an information sheet to provide information about the study prior to surgery as part of their pre-op packet. This will give patients an opportunity to review information on the study in the event they are diagnosed with an ileus and approached to participate.

Enrollment and Consent

Enrollment will take at the time of diagnosis of postoperative ileus. The patients will be asked to participate in the study after evaluation by either the PI or the co-investigators. The investigator and study coordinator will discuss the study with the patient and informed consent will be obtained. Patients will be assigned a unique study identification number.

Randomization

Randomization will take place following enrollment and consent. A numbered, sealed envelope, corresponding to the patients' assigned study number, will be opened by *the study coordinator* indicating to which study group the patient is randomized. The study coordinator will notify the pharmacy which study group the patient has been randomized to. Randomization will be stratified to open or laparoscopic surgery, location of surgery (right/left), stoma reversal and presence or absence of stoma. *This will be kept in a locked key to be revealed at the end of the study.*

Enhanced Recovery After Surgery Pathway

All patients will be managed via standardized accelerated postoperative recovery guidelines, which are currently in use by the division of colorectal surgery at UHCMC. This includes patient-controlled analgesia pump, oral analgesia and diet on the first postoperative day, early postoperative ambulation, and defined discharge criteria.

Study Methods

At the time of diagnosis of postoperative ileus and after enrollment and randomization, all patients will be returned to NPO status. Nasogastric tubes (NGT) may be placed for gastric decompression at the discretion of the surgical team if clinically indicated. In the event that an NGT is placed, medications will be given orally or via the NGT, which will be clamped for 30 minutes after administration. Patients will continue on standard ERAS pathways with the exception of reduction of diet. Antiemetics will be given as clinically indicated; however, no prokinetic or promotility agents will be given as scheduled dosages.

Patients randomized to the study group will be given 12mg of Entereg orally twice a day, from the time of diagnosis of postoperative ileus to the time of return of bowel function and tolerating solid food without vomiting or experiencing significant nausea within 4 h following the meal, or without having to revert to enteral fluids only or for 5 days.

Patients randomized to the control group receive standard postoperative care.

The patient and surgical team will be able to know which arm of the study the patient is in based on documentation in the medical record of the administration of Entereg.

Patients in both groups will remain NPO until the return of bowel function, defined as passage of stool, decrease in nasogastric tube output. At this point, the nasogastric tube will be removed and a trial of oral diet will be attempted per surgeon's discretion.

Standard discharge criteria will be applied to all patients, including:

- Passage of stool
- Ability to tolerate solid food and to drink comfortably
- Adequate oral analgesia
- Patient's willingness to be discharged.

Data to be collected

The medical/surgical information below will be collected as part of this research study and is all information already available as part of the patients medical chart.

- Patient name, medical record number
- Past Medical History

- Past Surgical history
- Preoperative Medications (including steroids, anticoagulation, opioid use)
- Pre-operative Diagnosis
- Patient Demographics (age, gender, BMI, ASA score)
- Procedure performed
- Time of surgery
- Wound classification
- Estimated blood loss
- Intraoperative transfusion
- Intraoperative IV fluids given
- Conversion from laparoscopic to open procedure
- Stoma creation
- Time/day surgery to ileus
- Time from surgery to medication given
- Time from ileus diagnosis to medication given
- Was there return of bowel function (flatus or stool, solid or liquid, stoma output) prior to ileus
- Intra-abdominal infection/anastomotic leak
- Time/day of return of bowel function post ileus (flatus and stool- solid or liquid, and stoma function)
- Time/day of ability to tolerate oral diet (liquid and solid food)
- Nasogastric tube placement and daily output
- Duration of nasogastric tube
- Use and type of anti-emetics given
- Total number of Entereg doses given
- Post operative complications including reoperation
- Length of stay in hospital, defined as time from surgery to discharge
- 30-day readmissions

The above collected data will be put into a REDCap (Research Electronic Data Capture) database which is a secure web application for managing online surveys and databases. It allows the safe and secure storage of research data including storage of PHI HIPAA identifier fields.

Study Completion

Completion of participation in the study will be 30 days after the date of surgery. Any readmission up to 30 days post-operatively to the hospital as a direct result of their surgery will be followed. The patients will follow-up with the surgeon in the office in approximately 3-6 weeks, which is considered standard of care for all patients undergoing colorectal surgery and is not considered part of the research study. Any patient for whom follow-up documentation is missing or incomplete shall be contacted via telephone. The purpose of the call will be to simply determine return to function and outcome. Only a co-investigator shall contact the subject and will identify themselves at the beginning of the call. Any subject can reserve the right not to participate in the phone call interview; they would remain in the study.

Patient Withdrawal

A subject has the right to withdraw from the study at any time for any reason without prejudice to their future medical care by the physician or the institution. The investigator and principal site also have the right to withdraw subjects from the study for the reasons listed below. Should a subject (or subject's legally authorized guardian/representative) decide to withdraw or be withdrawn, reasonable efforts will be made to complete and report the observations as thoroughly as possible.

Subjects may be removed from the study, if any one or more of the following events occur:

- Serious Adverse Event
- Noncompliance
- Lost to follow-up
- Investigator/Principal site recommendation

- Withdrawal of consent
- Protocol Violation
- Intercurrent illness
- The investigator considers it in the patient's best interest to do so

This study is estimated to take 24 months for completion.

Statistical Plan

After recruitment of 71 patients, a safety monitoring board comprised of members of the University Hospitals Faculty will evaluate data and adverse events to ensure that there are not ongoing safety concerns that might call for early termination of the study.

Variables/Time Points of Interest

The following data will be recorded as described in the Study Procedures:

- Patient name, medical record number
- Past Medical History
- Past Surgical history
- Medications (including steroids, anticoagulation, opioid use)
- Pre-operative Diagnosis
- Patient Demographics (age, gender, BMI, ASA score)
- Procedure performed
- Time of surgery
- Wound classification
- Estimated blood loss
- Intraoperative transfusion
- Intraoperative IV fluids given
- Conversion from laparoscopic to open procedure
- Stoma creation
- Time/day surgery to ileus
- Time from surgery to medication given
- Time from ileus diagnosis to medication given
- Was there return of bowel function (flatus or stool, solid or liquid, stoma output) prior to ileus
- Intra-abdominal infection/anastomotic leak
- Time/day of return of bowel function post ileus (flatus and stool- solid or liquid, and stoma function)
- Time/day of ability to tolerate oral diet (liquid and solid food)
- Nasogastric tube placement and daily output
- Duration of nasogastric tube
- Total number of Entereg doses given
- Post operative complications including reoperation
- Length of stay in hospital, defined as time from surgery to discharge
- 30-day readmissions

Statistical Methods

The study co-investigators and research team will perform statistical analysis. Routine statistical analyses will be utilized for parametric and non-parametric datasets, as appropriate. Demographic data will be analyzed using students t-test or Fishers exact test as appropriate. Categorical data will be analyzed using χ^2 analysis or Fishers exact test where applicable. Normally distributed data will be presented as means \pm SD of the mean, non-normally distributed data will be presented as medians \pm quartiles and categorical data will be presented as raw data and frequencies. A p value of < 0.05 will be considered statistically significant.

Power/Sample Size:

In our practice, patients undergoing open or laparoscopic colectomy without stoma creation who develop POI have a mean length of stay of 10.67 +/- 5.98 days compared to 4.86 days for patients who do not develop POI.

Using this information, to detect a significant decrease in length of stay by 3 days, with a 0.05 level of significance and a power of 80%, a total of 142 patients (71 patients per arm) are required.

Drug supplies (Entereg) for this study will be provided by Merck.

In the event that Merck is unable to provide drug supplies, the University Hospitals Case Medical Center Pharmacy will provide Entereg for this study.

The University Hospitals Case Medical Center Pharmacy will be responsible for distribution of drug in the treatment arm.

All adverse events will be reported per local IRB policy.

Reportable Problem: Any event which meets all three of the following criteria:

- Unexpected (in relation to the protocol and informed consent document),
- Related (in the investigator's opinion, the event has a 50% or greater chance of being related to the subject's participation in the study), and
- Gives evidence of new or increased risk to subject(s).

A reportable problem may include, but is not limited to, adverse events, protocol deviations, non-compliance, etc. Within 24 hours of knowledge of a reportable problem, the principal site must be notified. It is acceptable for the first notification to be a telephone conversation with the appropriate person at the principal site (leaving

All adverse events will be reported per local IRB policy.

Reportable Problem: Any event which meets all three of the following criteria:

- Unexpected (in relation to the protocol and informed consent document),
- Related (in the investigator's opinion, the event has a 50% or greater chance of being related to the subject's participation in the study), and
- Gives evidence of new or increased risk to subject(s).

A reportable problem may include, but is not limited to, adverse events, protocol deviations, non-compliance, etc. Within 24 hours of knowledge of a reportable problem, the principal site must be notified. It is acceptable for the first notification to be a telephone conversation with the appropriate person at the principal site (leaving a message is not sufficient) as long as the appropriately-completed CRF is submitted in a timely manner following the call.

Adverse Event (AE): Any new, undesirable medical experience or worsening of a pre-existing condition which occurs during study procedure or follow-up. Any and all adverse events, regardless of seriousness, that meet the above definition of a reportable problem, will be reported to the principal site within the timeframes indicated above.

For reportable adverse events, the following will be determined and recorded on the adverse event case report form:

- Onset Date and Resolved Date (unless continuing)
- Intensity/Severity
- Discontinued due to AE
- Relationship to Drug/Procedure
- Action Taken
- Outcome

The following guideline is suggested in determining the severity of each adverse event in this study:

- Mild – event is noticeable but transient, requires no treatment and does not interfere with the subject's daily activities.

- Moderate – event causes a low level of inconvenience or discomfort to the subject and may partially interfere with daily activities, and may require treatment.
- Severe – event causes a high level of inconvenience or discomfort to the subject, interrupts daily activities and requires treatment.

Protocol Deviation: Deviations from the protocol (whether by the subject or investigative staff) that meet the criteria of a reportable problem (i.e. give evidence of new or increased risk to subject[s]) will be reported to the principal site within the timeframes indicated above. Protocol deviations that do not meet the criteria of a reportable problem should be reported to the principal site within 5 calendar days of knowledge of their occurrence. Emergent and purposeful deviations from the protocol to mitigate risk to subjects should be reported to the principal site within 24 hours of occurrence. Less urgent, purposeful deviations from the protocol should receive prospective approval by the principal site.

Non-compliance: Non-compliance with regulations must be reported to the principal site within 24 hours of occurrence, regardless of the event's meeting the criteria of a reportable problem defined above.

Additional items requiring prompt reporting to the principal site (within 24 hours):

- Any subject complaints indicating new or increased risk to subject(s)
- Breach of subject confidentiality
- Imprisonment of a study subject during study participation

Responsibility of Principal Investigator:

- Analysis of Adverse Events with respect to their clinical relevance and cause relation.
- Evaluation of necessary protocol amendments
- Provisional evaluation of the final results in the form of a written report, which will be the basis for an investigator reviewed publication.

Responsibility of Study Coordinator:

- The Study Coordinator will be responsible for monitoring the conduct of the study and data management at each site to ensure completeness and accuracy of data.
- The Study Coordinator will collect completed CRFs for analysis.
- The Study Coordinator will also be notified of any serious adverse event within 24 hours of knowledge of the event.

Responsibility of Study Group:

- The Study Group comprised of the PI, CO-Is and study coordinator will collectively review and analyze the data.
- Each member of the Study Group is responsible to conduct the Study in full compliance with the protocol and make sure that data collection is complete and accurate.

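### Nasogastric tube status at randomisation is not defined as a baseline item, stratified on, or used in a pre-specified adjusted analysis

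*Combined protocol and SAP*

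**What the plan says.** Inclusion criteria and Recruitment give two alternative qualifying events, and one is enough: "1) return to NPO status after initial attempts at oral diet, 2) placement of nasogastric tube after surgery".

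The Randomization section lists the strata: "Randomization will be stratified to open or laparoscopic surgery, location of surgery (right/left), stoma reversal and presence or absence of stoma". All concern the operation or a stoma.

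Study Methods allows tubes after enrolment as well: "Nasogastric tubes (NGT) may be placed for gastric decompression at the discretion of the surgical team if clinically indicated". The same section says of blinding: "The patient and surgical team will be able to know which arm of the study the patient is in".

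Data to be collected includes "Nasogastric tube placement and daily output", "Duration of nasogastric tube" and "Time/day surgery to ileus", all taken from the medical chart. The list under Variables/Time Points of Interest repeats these items. Neither list has an item for the qualifying criterion or for tube status at randomisation.

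On the outcome, Study Overview states: "Primary outcome will be hospital length of stay". Statistical Methods offers routine parametric or non-parametric tests and names no covariate-adjusted or stratified analysis.

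**The concern.** A patient who needs decompression is plausibly further from discharge than one who has only been taken off diet. The protocol's own text points that way. Under Study Methods, falling tube output is part of how return of bowel function is recognised, and the tube comes out before diet is tried again. Tube status therefore bears on a secondary outcome and on the path to the discharge criteria.

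Two things are at stake. First, an unadjusted comparison of length of stay leaves in noise that a baseline covariate could remove. Second, the tube variable as listed mixes two kinds of event. A tube present at randomisation is a baseline characteristic. A tube placed afterwards is a decision by a team that can know the arm, and the drug may influence it: the background text reports fewer tube placements in the investigators' own experience of using the drug for ileus. Adjusting for a tube placed at any time could therefore remove part of a treatment effect or introduce bias.

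**Working it through.** **Inputs from the Power/Sample Size section.** SD of length of stay with ileus 5.98 days; target difference 3 days; significance level 0.05 (taken as two-sided); power 80%; 71 per arm.

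**Inputs assumed, because the documents give neither.** Share of patients with a tube at entry, p = 30% to 50%. Gap in mean stay between tube and no-tube entrants, D = 2 to 5 days.

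**The plan's own figure.** n per arm = 2 × (5.98 × (1.960 + 0.842) / 3)² = 62.4, so 63 per arm (126 in total). The t-test version gives 63.3, so 64 per arm (128 in total). The stated 142 is not reproduced, but it errs on the safe side: 71 per arm gives 84.3% power by t-test (84.8% by the normal formula). This does not affect the present point; it only sets the starting power.

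**Standard error of the unadjusted difference.** 5.98 × √(2/71) = 1.00 day.

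**Chance imbalance.** The SD of the between-arm difference in tube share is √(2p(1−p)/71), which is 0.077 at p = 30% and 0.084 at p = 50%. From two independent binomials of 71, the probability of an imbalance of 10 percentage points or more is 17% at p = 30% and 21% at p = 50%. Such a 10-point imbalance moves the estimate by 0.1 × D, or 0.2 to 0.5 day.

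**Gain from adjustment.** Formulas: SD of the shift in the arm difference = D√(2p(1−p)/71); R² = p(1−p)D²/5.98²; adjusted SD = 5.98√(1−R²); equivalent total N = 142/(1−R²). Power is by two-sided t-test at 71 per arm.

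| Tube share | Gap (days) | SD of shift (days) | R² | Adjusted SD | Adjusted SE | Power for 3 days | Equivalent N |
|---|---|---|---|---|---|---|---|
| 30% | 2 | 0.15 | 2.3% | 5.91 | 0.99 | 85.2% | 145 |
| 30% | 5 | 0.38 | 14.7% | 5.52 | 0.93 | 89.5% | 166 |
| 50% | 2 | 0.17 | 2.8% | 5.90 | 0.99 | 85.3% | 146 |
| 50% | 5 | 0.42 | 17.5% | 5.43 | 0.91 | 90.5% | 172 |

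**Is the shift extra to the standard error?** No. In the last row, 1.00² − 0.42² = 0.83, and √0.83 = 0.91, which is the adjusted standard error. The imbalance is a component of the 1.00 day, and adjustment removes it.

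**The case against.** The strongest reply is that the information is already collected and the test is already valid. Tube placement, daily output, tube duration and time from surgery to ileus are all charted, and the Study Calendar checks enrolment criteria at screening. A reader might infer that entry route goes unrecorded and can never be adjusted for. The documents do not support that: status at entry could probably be derived by setting tube days against the day of ileus. What remains is that no field is defined this way, that a tube placed on the day of randomisation may be ambiguous, and that reconstruction in an open-label trial analysed by its own team is weaker than a field completed before allocation is known.

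A reader might also infer that chance imbalance biases the result. It does not. It averages to zero under randomisation and is already in the 1.00-day standard error. The bias risk arises only if someone adjusts for tubes placed after randomisation, and no such analysis is planned.

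Nor is tube status the only marker of the ileus available at entry. Time to ileus and earlier return of bowel function are also recorded, and nothing shows that route predicts better than these.

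Finally, the severity gap is assumed. Tube placement is discretionary and may partly reflect surgeon habit. The routes overlap, since one or both criteria may be met and all patients are made NPO. The background text gives five days as the average extra stay from having an ileus at all, so a 5-day gap between two kinds of ileus patient is an extreme value. The low end of the table is worth about one point of power. All of this stands and limits the size of the point.

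**Conclusion.** The point holds as a matter of precision and of defining the variable. Tube status at randomisation is not stratified on, not defined separately from later tubes, and not in any pre-specified analysis. Under the assumed ranges, adjustment is worth the equivalent of about 3 to 30 extra patients and moves power for 3 days from about 84% to 85–90%. Actual power already exceeds the stated 80% on the plan's inputs, so the trial's viability is not in question. The figures also assume that the SD of 5.98, taken from colectomy patients without stoma creation, applies to the broader trial population and includes variation between routes. The possible bias from adjusting for an ever-placed tube cannot be sized from the documents. The change is worth making because it costs almost nothing and status at randomisation is most reliably captured prospectively.

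**What to change.** 1. Add to the eligibility form, completed before the envelope is opened: nasogastric tube in place at randomisation (yes/no), with date and time of placement, and the qualifying criterion or criteria met.
2. Pre-specify that field as a baseline covariate in the length-of-stay and time-to-bowel-function comparisons. If a rank test is chosen for length of stay, use a version stratified by this field.
3. Record tubes placed after randomisation separately, with date and time, and use them as an outcome only, never as a baseline covariate.

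The cost is one short form entry and one model covariate. No tube-placement rule or other care changes. For patients already enrolled, the field can be completed from the chart and marked as retrospective.

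Changing the strata is optional. If they are revised for other reasons, tube status could take the place of stoma presence, which has to be reconciled anyway with the exclusion of patients who have an ostomy. That would mean re-making the envelopes for patients not yet enrolled.
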